As the current study will provide long-term safety data to support data from the ongoing Phase III study in episodic cluster headache sufferers (19386A), the same dose of 400 mg eptinezumab will be administered in both studies. This dose has been selected based on the fact that cluster headache patients have higher CGRP levels compared to migraine patients and healthy controls²⁴, and a higher frequency of attacks compared to patients with migraine, suggesting that a higher dose of eptinezumab compared to the dose(s) approved for migraine prevention, is needed to alleviate features of the disease, related to the CGRP pathobiology. This together with PK and safety data from the completed Phase I studies in the migraine program,²⁹ in which eptinezumab was dosed up to 1000 mg and without any major safety findings, support that eptinezumab 400 mg can be safely used in the current study. This is in line with the dose considerations in the galcanezumab study in episodic cluster headache⁴³ which investigated the efficacy and safety of a dose which is almost three-folds the galcanezumab dose recommended for the treatment of migraine.^{41, 42}

Fulfilment of criteria for cCH, according to the eligibility criteria in this protocol, will be confirmed via prospectively collected information in the eDiary during the screening period, that is CH attack frequency of minimum 14 CH attacks for the 28-day Screening Period. The lower limit for CH attack frequency is in line with the IHS ICHD-3 criteria for CH. Clinical site staff will be given access to the eDiary data. Prior to enrolment, the investigator will review the data in the eDiary Eligibility Report to determine if the eligibility criteria are fulfilled.

Due to the high dose administered, the infusion time of eptinezumab is increased to 45 minutes in order to minimize the potential risk of hypersensitivity reactions associated with biologics.⁴⁴

All patients will receive four infusions of eptinezumab 400 mg at 12-week intervals. Given the eptinezumab half-life and proven efficacy over 12 weeks in migraineurs, it is considered that all patients will be exposed to eptinezumab for a period of approximately 1 year. Abortive and preventive treatments, as well as transitional therapies are allowed, or allowed with restrictions, during the study, hence no patient will be denied access to standard treatments.

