1.3 Exploratory Objective

To explore the target engagement of eptinezumab to CGRP.

2 Trial Design

This is an interventional, open-label, fixed-dose multiple administration trial to evaluate the long-term treatment with eptinezumab in participants with cCH.

An overview of the trial is presented in [Panel 1](#) and the scheduled trial procedures and assessments are summarized in [Appendix IV](#).

The target population for this trial is defined as participants with cCH, based on the *International Headache Society* International Classification of Headache Disorders third edition (IHS ICHD-3) classification, with documented evidence of cCH prior to screening and confirmed via prospectively-collected information in the eDiary during the Screening Period. A minimum of 14 cluster headache attacks must be captured in the eDiary for the 28-day Screening Period.

The total trial duration from the Screening Visit to the Safety Follow-up (SFU) Visit is approximately 60 weeks and includes Screening Period (4 weeks), Treatment Period (48 weeks), and SFU Period (8 weeks).

Eligible participants will receive four infusions with eptinezumab 400 mg at 12-week intervals at Day 0 (Visit 2), at the end of Weeks 12 (Visit 5), 24 (Visit 8) and 36 (Visit 11), administered as an intravenous (IV) infusion of 45 minutes (+15 minutes).

The SFU Visit will take place at Week 56 (Visit 15); that is, 20 weeks (5 half-lives) after the last eptinezumab administration.

Participants who withdraw from study, except for those who withdraw their consent, will be asked to attend a Withdrawal Visit as soon as possible and a further SFU Visit, scheduled 20 weeks (5 half-lives) after the last eptinezumab administration.

Participants who are withdrawn from the treatment will be given the opportunity to remain in the trial at the discretion of the investigator. Participants will be expected to attend all scheduled trial visits and procedures except eptinezumab administration. If participants refuse, they will be asked to attend a Withdrawal Visit as soon as possible and a further SFU Visit, scheduled 20 weeks (5 half-lives) after the last eptinezumab administration.

Eligibility will be assessed during the Screening Period and before the first administration of eptinezumab at the Baseline Visit (Day 0/Visit 2).

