
Objectives	Endpoints
Exploratory Objective 
To explore the target engagement of eptinezumab to calcitonin gene-related peptide (CGRP)	
Exploratory endpointChange from Baseline in CGRP (CGRP-eptinezumab complex, free CGRP) at Weeks 12, 24, 36, and 48

6 Analysis Sets

The following analysis sets will be used to analyse and present the data:

- all-participants-enrolled set* (APES) – all enrolled participants
- all-participants-treated set* (APTS) - all participants in the APES who received infusion with eptinezumab
- full-analysis set* (FAS) - all participants in the APTS who have a valid assessment of the baseline number of weekly attacks and a post-baseline assessment of number of weekly attacks.

The participants and data will be classified into the analysis sets during a *Classification Meeting* according to the definitions above after the trial database has been released, but prior to the headline results meeting.

Safety analyses (including tolerability and exposure), disposition, demographics and baseline characteristics will be based on APTS.

Efficacy analyses will be based on FAS.

Three Data Point Sets (DPS) will be used for presenting the results using eDiary data:

- DPS1: All data points obtained at or after enrolment
- DPS2: All data points obtained at or after enrolment except for those following the 7-day rule after the use of transitional treatment (for details see section 23.2.4)
- DPS3: All data points obtained at or after enrolment except for those following the 7-day rule after the use of transitional treatment (see section 23.2.4) and those following the 12-week rule after withdrawal from treatment (see section 23.2.1.5)

DPS1 will be used for the descriptive statistics described in chapter 7 as well as the sensitivity analyses described in sections 13.5.9.1 and 13.5.9.2, DPS2 will be used for the short-term efficacy estimand described in section 13.5.1, and DPS3 will be used for the long-term efficacy estimand (section 13.5.3), the sensitivity analysis described in section 13.5.9.3, and analyses based on eDiary data. For more details see chapter 13.

For efficacy data not derived from the eDiary all analyses will be based on all data points obtained at or after enrolment.

7 Descriptive Statistics

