13.5.9 Sensitivity Analyses of Secondary and Exploratory Endpoints

13.5.9.1 Sensitivity Analyses to assess the impact of the use of transitional medication

To assess the impact of the use of transitional treatments, the MMRMs described in sections [13.5.1](#) and [13.5.3](#) will be used to analyse data where all data are included also immediately after receiving a transitional treatment corresponding to a treatment strategy. It will only be done for the endpoints described in sections [13.5.1](#) and [13.5.3](#) respectively.

13.5.9.2 Sensitivity Analyses to assess the impact of the strategy of handling withdrawal from treatment

To assess the impact of the chosen hypothetical strategy for handling withdrawal from treatment the MMRM described in section [13.5.3](#) will be used to analyse data where all data

are included corresponding to a treatment strategy. It will only be done for the endpoint described in section 13.5.3.

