23.2.1.6 Calculation of Assessments for Sensitivity Analyses

When doing the sensitivity analyses of the use of transitional treatment and withdrawal from treatment data will contain all data when considering the prorating.

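### For the long-term estimand, the sensitivity analyses in SAP 13.5.9.1 and 13.5.9.2 are one and the same run, so neither isolates the strategy it is meant to test

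*SAP*

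**What the plan says.** SAP chapter 6 defines three data point sets for eDiary data. DPS1 has no exclusions. DPS2 leaves out data caught by the 7-day rule after transitional treatment. DPS3 leaves out those data and also "those following the 12-week rule after withdrawal from treatment". The short-term estimand (13.5.1) is estimated on DPS2 and the long-term estimand (13.5.3) on DPS3.

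Two sensitivity analyses are then given separate purposes. Section 13.5.9.1 is to show the impact of transitional treatment. Its data are "included also immediately after receiving a transitional treatment corresponding to a treatment strategy", and on scope it says "It will only be done for the endpoints described in sections" 13.5.1 and 13.5.3. Section 13.5.9.2 opens "To assess the impact of the chosen hypothetical strategy for handling withdrawal from treatment". It re-runs the 13.5.3 model on all data, for the 13.5.3 endpoint only.

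Chapter 6 assigns the data set for both: "DPS1 will be used for the descriptive statistics described in chapter 7 as well as the sensitivity analyses described in sections 13.5.9.1 and 13.5.9.2". SAP 23.2.1.6 covers both with one handling rule: "data will contain all data when considering the prorating".

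**The concern.** A sensitivity analysis that is said to test one assumption should change that assumption and hold the rest fixed. The long-term main analysis makes two: it sets aside data after transitional treatment, and it sets aside data collected long after the last infusion in participants withdrawn from treatment. The SAP promises a check on each, but what it specifies is a single run that drops both assumptions at once.

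Two things are at stake. One number could be reported twice and read as two independent robustness checks. And a small difference between that number and the main result would not show that either assumption is harmless, because two shifts of opposite sign could offset each other.

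**Working it through.** The plan gives no figure on this point, so the check is a comparison of specifications, followed by what each comparison can and cannot identify.

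**Step 1. Set the runs side by side.** Mark each diary data point T if the 7-day rule removes it and W if the 12-week rule removes it.

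| Run | Model and endpoint | Population | Data set | Prorating | Main set | Points restored |
|---|---|---|---|---|---|---|
| 13.5.9.1, short-term | 13.5.1 MMRM, Weeks 1-4 | FAS | DPS1 | all data | DPS2 | T only; T and W |
| 13.5.9.1, long-term | 13.5.3 MMRM, Months 1-12 | FAS | DPS1 | all data | DPS3 | T only; W only; T and W |
| 13.5.9.2 | 13.5.3 MMRM, Months 1-12 | FAS | DPS1 | all data | DPS3 | T only; W only; T and W |

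Sources: SAP chapter 6 (data sets, FAS), 13.5.1.2 and 13.5.3 (models), 13.5.9.1, 13.5.9.2 and 23.2.1.6. The last two rows agree in every element. The first row changes only the transitional rule, as intended.

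**Step 2. Can both rules remove data?** Yes. Protocol 3.2 says "Abortive and preventive treatments, as well as transitional therapies are allowed, or allowed with restrictions, during the study". For participants withdrawn from treatment who remain in the trial, SAP chapter 2 says "Participants will be expected to attend all scheduled trial visits and procedures except eptinezumab administration". Two worked cases, assuming an otherwise complete diary, seven-day weeks from Day 0 and infusions on schedule:

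- Transitional treatment on Days 33, 34 and 35. The rule in 23.2.1.5 removes Days 34 to 42. These days touch the weekly entries for Week 5 (Days 28-34), Week 6 (Days 35-41) and Week 7 (Days 42-48). One of four weeks is left, so Month 2 is missing under 23.2.1.3, which needs at least two.
- Withdrawal from treatment after 1, 2 or 3 infusions with follow-up to Week 48. Counting 84 days from the latest infusion, as 13.5.3 does, exclusion starts on Day 84, 168 or 252. It removes (336 - 84)/7 = 36, (336 - 168)/7 = 24 or (336 - 252)/7 = 12 weekly scores.

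**Step 3. What the combined run identifies.** For a simple mean, ignoring points that are both T and W, let m3 be the DPS3 mean, pT and pW the shares of DPS1 points flagged T and W, and dT and dW their mean distances from m3. Then

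DPS1 mean - m3 = pT x dT + pW x dW.

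This is one observed difference with two unknown terms, and it is zero whenever pT x dT = -pW x dW. The MMRM weights data differently, but it faces the same problem of attribution.

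**Step 4. Likely signs.** SAP 13.5.1.1 expects transitional treatment to help and calls excluding those data conservative, so restoring them should enlarge the reduction. SAP 13.5.3 expects most of the eptinezumab effect within 12 weeks of the last infusion, so restoring later off-treatment data would plausibly shrink it. The second sign is an inference from that sentence; the SAP does not state it.

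**Step 5. Illustration with assumed inputs.** The documents give none of the following. Assume 125 participants, baseline averaging 40 attacks a month, a 35% underlying reduction, 8% of participant-months flagged T, and 15 participants withdrawn from treatment but still followed. Shifts are in percent of baseline. Estimates are simple averages of monthly means, not the MMRM, from one simulated data set per row.

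| Assumed shift: T, W | DPS3 | DPS2 | DPS1 | DPS3 to DPS2 | DPS2 to DPS1 | DPS3 to DPS1 |
|---|---|---|---|---|---|---|
| -30%, +30% | -13.53 | -12.76 | -13.66 | +0.77 | -0.90 | -0.13 |
| -30%, 0 | -13.58 | -13.43 | -14.16 | +0.15 | -0.73 | -0.58 |
| 0, +30% | -13.44 | -12.79 | -12.79 | +0.65 | 0.00 | +0.65 |

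In the first row two shifts of 0.77 and 0.90 attacks a month leave a combined difference of 0.13. The +0.15 in the second row is chance, since no withdrawal effect was put in. The table shows the mechanism and is not evidence of size in this trial.

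**The case against.** The best textual defence is to read 13.5.9.1 on its own as restoring only the data just after transitional treatment, with the 12-week exclusion kept. Chapter 6 and 23.2.1.6 rule that out: the run is assigned to DPS1 with all data, and no set applying only the 12-week rule is defined.

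The stronger objection is about consequence. The trial is single-arm, its primary objective is safety, there are no key secondary endpoints, and SAP 13.2 plans no formal testing. DPS1 against DPS3 is still a legitimate combined treatment-policy contrast; what is lost is attribution. Section 13.5.5 also tabulates how many participants had each intercurrent event, so a reader could see if one was rare. Off-treatment data may be scarce: Protocol 8.7 stops new data collection after withdrawal from the study, apart from the Withdrawal and Safety Follow-up Visits and adverse event follow-up, and remaining after treatment withdrawal is at the investigator's discretion. All of this stands and limits the severity. It does not remove the point, because event counts do not show how far each strategy moves the estimate, and nothing in the plan ensures that either kind of excluded data is negligible.

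A reader might also infer that the withdrawal rule dominates, since a single-day transitional use costs only 1 or 2 of 48 weekly scores. The documents do not support that ranking: a three-day course can already make a month missing, and no frequency is given for either event.

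**Conclusion.** The point holds for the long-term estimand. Followed exactly, the SAP produces one combined result under two headings, and that result meets neither stated single-factor purpose unless one of the two rules happens to remove no data. Partial cancellation is plausible from the SAP's own expectations, but its size cannot be derived, because the documents give no rate of transitional use or of off-treatment follow-up.

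Three stronger readings should be resisted. A reader might infer that the long-term estimate itself is compromised; the duplication does not touch the DPS3 analysis. A reader might infer that 13.5.9.1 fails altogether; its short-term part, DPS1 against DPS2, is a valid one-factor comparison. And a reader might infer that the two shifts will cancel; the documents make this possible and do not show it. Severity is minor to moderate.

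**What to change.** 1. Run 13.5.9.2 on DPS2, which is already defined, and keep the long-term part of 13.5.9.1 on DPS1.
2. Report the long-term results stepwise. DPS3 to DPS2 restores the W-only points and changes only the withdrawal rule. DPS2 to DPS1 restores the T-flagged points and changes only the transitional rule. Label DPS3 to DPS1 as the combined treatment-policy contrast. State in 13.5.9.1 that its long-term comparator is the DPS2 run.
3. Amend the text to match: the data set assignment in chapter 6; the wording in 13.5.9.2 that puts every data point in; and the prorating rule in 23.2.1.6, so that the 13.5.9.2 run prorates on data left after the 7-day exclusion.

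A fourth data set applying only the 12-week rule is optional. It would give the transitional contrast with the withdrawal rule kept, which the stepwise order does not.

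Sections 13.5.3 and 23.2.1.5 also disagree on where the 84 days start, and the SAP is unclear on which reasons for withdrawal count. Both concern the definition of DPS3 and should be raised as a separate finding.

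Cost: a data set reassignment and text edits. Three sensitivity runs are listed now (13.5.9.1 short-term, 13.5.9.1 long-term, 13.5.9.2) and three remain, the last two now giving distinct results. No new data are needed.

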- The DPS2 will be replaced by DPS3
- The contrast that will be used is given as [1, 1] [1, 2] [1, 3] [1, 4] [1, 5] [1, 6] [1, 7] [1, 8] [1, 9] [1, 10] [1, 11] [1, 12] /divisor = 12

13.5.4 Rationale for the Efficacy Endpoints following the strategy of the Long-term Efficacy Estimand

Regarding the efficacy endpoints based on the number of cluster headache attacks, intensity of pain or use of abortive medication, the data handling will follow the strategies described in section 13.5.3. For all of these endpoints, the intercurrent events use of transitional treatment

and interruption or termination of IMP such that full dose is not received and withdrawal from treatment will be handled as described in section [13.5.3](#).

For endpoints based on the number of attacks the rationale is the same as previously described. For endpoints based on intensity of pain the same strategies are used since not getting the full dose (by interruption/termination of IMP or withdrawal from treatment) is expected to also affect the pain as well as use of transitional treatment is expected to decrease the pain severity.¹ For endpoints based on the use of abortive medication, not getting the full dose (by interruption/termination of IMP or withdrawal from treatment) is expected to also affect the use of abortive medication. Furthermore, the use of transitional treatment is expected to reduce the number of attacks and therefore is also expected to reduce the number of times abortive medication can be used.

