13.5.6.3 Other Efficacy Endpoints

Endpoints that are not covered by sections [13.5.6.1](#) and [13.5.6.2](#) will only be summarized descriptively as described in chapter [7](#).

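### The SAP routes conversion, remission and maximum-mild pain to both DPS1 and DPS3, so one diary can be classified two ways

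*SAP*

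**What the plan says.** SAP chapter 6 defines the data point sets used for eDiary results. The first is "DPS1: All data points obtained at or after enrolment", with no exclusions. DPS3 removes data under a 7-day rule after transitional treatment and a 12-week rule after withdrawal from treatment. The details of both rules are in 23.2.1.5.

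**Route to DPS1.** SAP 13.5.6.3 says that endpoints outside 13.5.6.1 (the MMRM list) and 13.5.6.2 (response and sustained response) "will only be summarized descriptively as described in chapter" 7. Conversion, remission and maximum-mild pain are in neither section. Chapter 6 adds that "DPS1 will be used for the descriptive statistics described in chapter" 7.

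**Route to DPS3.** SAP 13.5.4 adopts the 13.5.3 strategies for a whole class of endpoints: "Regarding the efficacy endpoints based on the number of cluster headache attacks, intensity of pain or use of abortive medication". For the estimator, 13.5.3 says "The DPS2 will be replaced by DPS3". Chapter 6 also says "DPS3 will be used for the long-term efficacy estimand (section 13.5.3), the sensitivity analysis described in section 13.5.9.3, and analyses based on eDiary data".

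**Silence elsewhere.** Sections 23.2.1.8 (conversion), 23.2.1.9 (remission) and 23.2.8 (maximum pain severity) name no data point set. Section 23.1 says that conversion and remission do not fit its three data structures, and it names no set either. By contrast, 13.5.6.1 and 13.5.6.2 both name DPS3.

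**The concern.** Two programmers can each follow the SAP correctly and derive these endpoints from different data. Conversion and remission are secondary efficacy endpoints, and maximum-mild pain is exploratory. The trial has no control arm, so the percentages will be read as they stand.

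The data on which the two sets differ can arise. Protocol Appendix II disallows occipital nerve block and headache steroids only for 30 days before screening and during screening, so they can be used on treatment. SAP 13.5.1.1 regards transitional treatment as able to alter disease status considerably, which is why it is handled by a hypothetical strategy. Participants withdrawn from treatment may stay in the trial, so diary data beyond 12 weeks after the last infusion can also exist.

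No planned output would show the difference. The sensitivity analyses on all data (13.5.9.1 and 13.5.9.2) cover only the endpoints of the two main efficacy estimands.

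**Working it through.** **Rules used**
- Week w covers days 7(w-1) to 7w-1, with the first infusion on day 0 (23.2.1.4: an infusion day starts a new week).
- On DPS3, days 1-7 after transitional treatment are removed, and a weekly entry is removed if it contains any such day (23.2.1.5).
- Remission: at least 4 consecutive weeks, first and last week with 0 attacks, all observed weeks with 0 attacks, at most 1 missing week (23.2.1.9).
- Conversion: first and last week with 0 attacks, at least 50% of weeks observed, at least 13 weeks of 0 attacks or missing data (23.2.1.8, which also mentions 12 weeks).
- Maximum-mild: a week with 0 attacks counts as mild or less (23.2.8).
- Assumption: a removed week counts as missing. The SAP does not say.

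**The plan's own figure.** 0.5 x 13 = 6.5, rounded up to 7, reproduces the 7 observed weeks stated in 23.2.1.8. With 12 weeks it would be 6.

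**Illustrative diaries, each run on both sets.** Weeks not listed as attack-free have attacks.

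| Diary | Treatment day | Attack-free weeks | Removed on DPS3 | DPS1 | DPS3 |
|---|---|---|---|---|---|
| A | 41 (last day of Week 6) | 7-10 | days 42-48 = Week 7 | remission: yes | no |
| B | 41 | 5, 6, 8, 9 (attack in Week 7) | Week 7 | remission: no | yes |
| C | 111 (last day of Week 16) | 17-29 | days 112-118 = Week 17 | 13-week conversion: yes | no |
| D | 125 (last day of Week 18) | 17-29 except Week 19 | days 126-132 = Week 19 | 13-week conversion: no | yes |
| E | 150 (in Week 22) | 17-29 | days 151-157, so Weeks 22 and 23 | 13-week conversion: yes | yes |
| F | 37 (in Week 6) | 6, 7 | days 38-44, so Weeks 6 and 7 | maximum-mild: met | not assessable |

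**Why each result follows**
- A: DPS1 has a 4-week run. On DPS3 the run cannot start on missing Week 7, and Weeks 8-10 are only 3 weeks.
- B: DPS1 has two runs of 2 weeks. DPS3 sees Weeks 5-9 with one missing week, which the remission rule allows.
- C: on DPS3, Weeks 18-29 are 12 weeks, one short of 13. With a 12-week threshold both sets give yes.
- D: on DPS1 the longest run is Weeks 20-29, 10 weeks. On DPS3, Weeks 17-29 are 13 weeks with 12 observed, above the 7 required.
- E: 11 of 13 weeks are observed, and the two removed weeks are bridged as missing.
- F: on DPS1 both weeks have 0 attacks. On DPS3 neither has data.

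**The case against.** The best defence is that the SAP separates format from data. Chapter 7 sets out which statistics to print and does not say which diary days enter a derivation. Section 13.5.4 is the specific data rule and its wording covers these endpoints. Chapter 6 gives DPS3 to eDiary analyses and refers the reader to chapter 13 for detail. Deriving on DPS3 and tabulating in chapter 7 format would satisfy most of the text.

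That is probably the intention, and the fix adopts it. It does not remove the conflict. Chapter 6 itself ties the chapter 7 descriptives to DPS1, and 13.5.6.3 uses the same chapter 7 reference. The two neighbouring sections name DPS3, while 13.5.6.3 names nothing.

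A reader might infer that DPS1 simply inflates eptinezumab's remission and conversion rates and that DPS3 would lower them. The rules do not support that. Diaries B and D move the other way and E does not move. Nor does DPS3 remove all credit for transitional treatment: it drops only 7 days after use, later attack-free weeks still count, and the conversion rule lets removed weeks sit inside a run.

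The limited stakes also stand. The primary objective is safety, there are no key secondary endpoints, and no formal testing is planned.

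**Conclusion.** The contradiction is in the current SAP text, and it can change whether a participant counts as a remission, a conversion or a maximum-mild week. Reported rates can move either way. Remission is the more sensitive of the two run-based endpoints, because it tolerates only one missing week. Conversion often survives a single mid-run use.

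The size of the effect on the percentages cannot be computed, because neither document gives a rate of transitional use. A reader might try to bound it from the prednisone result cited in SAP 13.5.1.1 (35% against 7% cessation, an excess of 28 points) times a guessed share of users. That would not bound it. The cited trial was in episodic cluster headache and measured cessation at 7 days, whereas remission here needs at least 4 weeks. It also estimates what steroids do to attacks, whereas the DPS1-DPS3 difference depends on where the removed weeks fall in a run.

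The diaries are constructed examples and treat removed weeks as missing. They show that classification can change, not how often. The 12-week withdrawal rule creates the same split in principle, but no example of it was worked. This should be corrected before the tables are programmed.

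**What to change.** 1. In SAP 13.5.6.3, state that conversion, remission and maximum-mild pain are derived on FAS and DPS3 in line with 13.5.4, and that the same table on DPS1 is shown as a sensitivity summary.
2. In chapter 6, limit the DPS1 clause to descriptive tables of observed eDiary values.
3. In 23.2.1.8 and 23.2.1.9, state how weeks removed by the 7-day and 12-week rules count in a run, so that a removed week with reported attacks is not bridged as attack-free. With that rule, diary B is not a remission and diary D is not a conversion on either set.

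The cost is a few sentences and one repeat of an existing table. The rates may change slightly, in either direction.
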